### **Survey Administration.**

The PI and/or Project manager (unblinded) will administer the following surveys after the clinician has signed informed consent: Demographic and professional history; PCMI.

The RA (blinded) will be responsible for all patient data collection.

Surveys, Diaries, Testing, Interviews and Fidelity Checks	Type of Data; how collected	Who will collect	Data source	Pre - visit 1 (V1 )	Visit 1 Baseline	Within 24 hours of V1	Visit 2 ~ 4 weeks after V1	Visit 3 ~ 4 weeks after V2	Visit 4 ~ 4 weeks after V1	Post-trial
Asthma Control Questionnaire – 6 items (ACQ6) without item 7 (FEV1)	Survey; Collected by phone	RA or PM	Patient	X						
Demographics	Survey; Collected by phone	RA or PM	Patient	X						
Conventional and Alternative Management for Asthma (CAM-A)	Survey; Collected on tablet	RA	Patient	X					X	
Asthma history	Survey; Paper and pencil	RA	Patient		X					
Forced Expiratory Volume in One Second (FEV1) alone – item & on the ACQ	Non-invasive measure of airflow obstruction; hand-held spirometer	RA	Patient; hand-held spirometer		X					
Newest Vita Sign (NVS)	Survey; Paper and pencil survey	RA	Patient		X					
Shared Decision Making Questionnaire- 9 items (SDMQ9)	Survey; Paper and pencil	RA	Patient		X					
Medication Adherence Record Scale-Asthma (MARS-A)	Survey; Paper and pencil survey	RA	Patient		X		X	X	X	
Patient reported Outcome Measurement Information System- 29 items (PROMIS-29)	Survey; Paper and pencil survey	RA	Patient		X		X	X	X	
Asthma Quality of Life Questionnaire (AQLQ)	Survey; Paper and pencil survey	RA	Patient		X		X	X	X	
Patient Immediate post-visit debriefing and blinding assessment	Survey; Paper and pencil	RA	Patient		X					
Asthma Control Questionnaire – 7 items (ACQ7) with FEV1	Survey and non-invasive measure of airflow obstruction; Paper and pencil and hand-held spirometer	RA	Patient; hand-held spirometer				X	X	X	
Asthma daily diary	Diary; Paper and pencil	Patient	Patient		DISPENSED		X	X	X	
Doser electronic dose counter	Electronic dose counter	RA will download by hand	Patient; Doser electronic counter		DISPENSED		X	X	X	
Client Satisfaction Questionnaire 8 items (CSQ8)	Survey; Paper and pencil	RA	Patient						X	
Post-trial interviews	Interviews, Audio recorded	PI	Patients, loved ones and providers							X
Provider Data Collection Form	Survey; Paper and pencil	PM or PI	Providers	X						
Provider Co-Management Index (PCMI)	Survey; Paper and pencil	PM or PI	Providers	X						
Readiness Ruler	Scale; Collected on tablet	Provider	Patient		X					
Provider Immediate post-visit debriefing	Survey; Paper and pencil	RA	Providers		X					
Brief Negotiated Intervention (BNI) Adherence Scale (Active condition)	Fidelity Checklist	Coder (TBD)	Audio files of patient-provider visits			X				
Fidelity Check Attention control condition	Fidelity Check	Coder (TBD)	Audio files of patient-provider visits			X				

**Intervention Condition.** PCPs randomized to **BREATHE** will receive the tablet which, when the screen is advanced by the PCP, will prompt the PCP through a 7-minute, 4-step brief intervention tailored to respond to the patient's specific beliefs endorsed on the CAM-A using content identified in our CBPR development phase (focus groups). See the Brief Negotiated Intervention (BNI) for the full intervention details.

**Step 1: Raise the subject (1½ minute).** PCP establishes rapport using persuasive communication techniques and assesses the patient's disease knowledge, perception of asthma control, quality of life (QoL), self-care preferences, and motivation for enhanced asthma control, exploring specific beliefs that may affect adherence.

**Step 2: Provide feedback (1½ minutes).** PCP provides feedback to the patient based on assessments made in the prior step. The PCP candidly discusses the patient's uncontrolled asthma and specific beliefs in the context of ICS non-adherence, drawing a connection between current symptoms and ICS non-adherence.

**Step 3. Enhance motivation (2 minutes).** The PCP attempts to enhance the patient's motivation to increase ICS adherence using motivational interviewing techniques such as collaboration, empathy, concern, and acceptance of ambivalence about self-management. In this step, the PCP may elicit the patient's beliefs regarding the benefits, and negative sequelae, of their current self-management approach (pro/con).

**Step 4: Shared decision-making (2 minutes).** The PCP and patient jointly consider treatment options. The PCP will actively attempt to build consensus around ICS adherence, reconciling conflicts to better align beliefs with evidence-based guideline-directed ICS treatment. For example, if the patient uses ICS intermittently (rather than the required twice-daily dosing) because of an erroneous belief that tolerance to ICS develops with daily dosing, then the PCP will attempt to counter that belief using responses gleaned from the CBPR development phase (focus groups) and information from national guidelines. This will likely include encouraging the patient to use ICS once a day (50% adherence) as an initial short-term plan to be followed by a return visit and re-evaluation of asthma control. If the patient declines to engage in shared decision-making or declines attempts at negotiating ICS use, then the PCP and the patient agree to disagree. This is a one-time intervention.

**Usual care with an attention control condition.** Patient codes associated with PCPs randomized to the attention control condition will trigger the tablet to load a 7-minute timer for the PCP to use to track the length of the attention control condition (discussion of healthy lifestyles). Control PCPs will have access to all the data that the active intervention PCPs have: the ACQ score, CAM-A results, and lung function results. To control for contact, they will be instructed to engage in a 7-minute diet and exercise discussion as this will not confound results and it was a common topic in our prior study; ICS adherence was not discussed.

**Intervention Training for BREATHE PCPs.** We will train PCPs randomized to the **BREATHE** condition using procedures we have used before with content gleaned from our CBPR development phase (focus groups and PCP review) as described previously. The core training for PCPs delivering the **BREATHE** intervention will be conducted by our consultant, [name], and will consist of one, 2-hour instructional session: 30 minutes of didactic instruction addressing the delivery of the 4 steps of the brief intervention; 10 minutes of role-playing of commonly encountered scenarios and; a 50 minute skills workshop in which PCPs role play creating a trusting environment, relinquishing sole decision-making, motivating and empowering patients to engage in self-management decisions. A question and answer period will conclude the training. PCPs will receive a laminated action card that fits in a lab coat pocket summarizing the intervention steps as a resource although the steps of the intervention will be available to the PCP on a tablet during the visit.

Immediately after training, PCPs will be tested using a standardized patient scenario to demonstrate that he/she can deliver the intervention in 7 minutes or less. All testing will be audiotaped and a trained rater will determine

whether the critical elements of the brief intervention were completed in 7 minutes using the validated Brief Negotiation Interventions Adherence Scale (BAS) adapted to asthma (see draft BNI protocol and BAS). If the PCP fails testing, she/he will receive additional instruction and retested. Prior studies have shown that such remediation re-training results in 100% proficiency. PCPs will be encouraged to informally try out some of these techniques before the study goes live. The Consultant will follow-up with each PCP to answer questions from this “dry run” before the first subject is enrolled.

**Intervention Fidelity.** To evaluate adherence to the treatment protocol, all **BREATHE** visits will be audiotaped. The Project Manager (who is not blinded) will review all audio files within 24 hours of the visits at which time she will complete the Brief Negotiated Intervention Adherence Scale (BAS) to evaluate drift, when in the visit (beginning, middle, end) the intervention is delivered, as well as the length of the **BREATHE** sessions. The Consultant [name] will conduct additional training to enhance intervention fidelity and brevity if problems are identified. PCPs will not be excluded from the study if they fail to deliver all elements or require more than 7 minutes to deliver **BREATHE**; this feasibility metric will be tracked.

**Fidelity to the attention control condition.** PCPs randomized to the control intervention will not receive any specific training but audio files will be reviewed by the Project Manager (who is not blinded) within 24 hours of the visit to ascertain the content and length of the healthy lifestyles discussion (the attention control condition), as well as to listen for any evidence of contamination (use of the 4-step shared decision making intervention using motivation interviewing techniques). Feedback to improve fidelity to the attention control condition, if needed, will be made promptly after reviewing the audio files.

**Anticipated Problems and Strategies.** If time does not allow for rapid review of all audio files, 20% will be randomly selected to be rated by the Project Manager: all 1st visits will be rated, and at least one additional file per PCP will be reviewed prior to enrollment of their 5th patient subject. We will minimize contamination within FQHCs by (1) training only **BREATHE** PCPs to deliver the active intervention and (2) encouraging PCP confidentiality regarding training and intervention content. We will also review audio files of the attention control condition to assess for contamination.

**Final assessment and refinement of the intervention.** We will conduct nested cohort interviews with five patient subjects and five family/support person of enrolled subjects post-trial to ascertain their reactions to the intervention. An additional five patients will be interviewed who were lost to follow-up to better understand what it was that prevented their continued participation. A purposive sample of ~ 6 PCPs (2-4 who participated in the **BREATHE** intervention and two who declined participation, should we have any) will also be interviewed to better understand their perspectives about the intervention or their clinical settings that facilitated or prevented study participation. The PI will conduct the interviews and data will be analyzed as described in the methods section.

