**Patient Participants & Consent.** We will enroll 80 Black adults with uncontrolled asthma (10 / PCP). The study team will read the informed consent and when subjects have had all questions addressed, they will be asked to sign indicating they are entering the study voluntarily. Consent will be obtained the RA who is blinded.

**Inclusion Criteria:** Patients must be 1) adults ( $\geq 18$  years of age) who self-report race as Black or African American; 2) with PCP-diagnosed persistent asthma; 3) prescribed ICS; 4) receiving asthma care at participating FQHCs; 5) who have uncontrolled asthma (defined below) ; and 6) have erroneous personal health and/or negative ICS beliefs (defined below).

Interested participants who meet the first 4 criteria will be screened for uncontrolled asthma by administering the Asthma Control Questionnaire (ACQ) by phone (phone administration is both reliable and valid). The ACQ includes 6 self-reported items about asthma symptoms and an objective measure of pulmonary function:

the forced expiratory volume in one second (FEV1). The ACQ has demonstrated validity and reliability with and without the use of the FEV1. ACQ scores  $\geq 1.5$  have a positive predictive value of 88% in identifying uncontrolled asthma in clinical trials. PCPs will be notified of all patients with ACQ scores  $\geq 1.5$  and patients will be scheduled for a follow-up visit with their PCP as these scores indicate that asthma is not in good control. At that visit, if they remain interested in enrolling in the trial, they will be screened for beliefs associated with ICS non-adherence using the CAM-A instrument, administered on customized tablet that allows for immediate scoring. patients will complete the 17-item CAM-A which will self-score. Any one endorsement of a non-prescription asthma management preference or negative ICS belief is considered a positive screen and the patient is eligible for enrollment in this two-step screening process (+ ACQ screen by phone and + CAM-A screen at visit). At this visit, trained study staff will also obtain the FEV1 using a hand held spirometer calibrated daily, as well as additional surveys (see Table 1).

**Exclusion Criteria:** 1) participation in Phase 1 of the **BREATHE** trial (focus groups); 2) non-English speaking; 3) serious mental health conditions (e.g., psychosis) that preclude completion of study procedures or confound analyses.

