**Enrollment feasibility.** The two FQHCs provide primary care to over 100,000 unique patients a year, who are cared for by 50 providers. Each provider sees approximately 2,000 asthma patients. Using a conservative estimate of 8% asthma prevalence, 160 unique patients with asthma are served per provider. Based on our preliminary studies we expect ~69% of subjects screened will have uncontrolled asthma (n=110 patients / PCP); of these, 97% will screen positive on the CAM-A yielding 107 eligible patients / PCP. Thus, we have an adequate patient pool from which to draw 10 patient subjects / PCP.

**Blinding.** Patient codes, tied to PCP assignment (active vs. control), will be entered into a tablet prior to the completion of the CAM-A by the RA. The meaning of these codes will not be known to the RA. Using these codes, the software will trigger the tablet to load either the **BREATHE** intervention steps or the attention control timer (described below) after the CAM-A has been completed. These screens will be hidden from the patient and the RA by two “hold” screens warning the RA/patient subject not to advance further. We will assess the adequacy of blinding of the subject and the RA as a process outcome at the end of the study. Both active and control PCPs will receive the tablet from the RA and the results of the lung function testing (FEV1). The RA will set up two digital recorders to capture the audio of the office visit and then leave the room. The RA will be instructed to stay close by to monitor the end of visit but not close enough to overhear the conversation. The statistician ([name]) will be blinded. The PI, Project Manager and database manager will not be blinded.

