## **STATISTICAL PROCEDURES**

**Patient data collection.** While we recognize the need for longer follow-up in a full-scale RCT, trained RAs, blind to treatment status, will collect data four times: baseline and 1-month, 2-month, and 3-month follow-up. To address the risk of assessment reactivity, both groups will receive an equal number of assessments.

**Patient subject measures (see Table 1).** The primary outcome measure is patient-reported asthma control over 3 months as measured with the ACQ. We will collect the ACQ and secondary outcomes including objective measures of airflow obstruction (FEV1), asthma QoL using the Asthma Quality of Life Questionnaire - AQLQ and ICS adherence using the Medication Adherence Record Scale-Asthma (MARS-A). The MARS-A correlates with objective ICS adherence as measured by electronic monitoring and ICS fill/refill claims data. Other surveys that will be used to characterize the subjects include the asthma history, Newest Vital Sign, the PROMIS-29 and the Shared Decision Making Questionnaire- 9 items. All patient subjects will

also be asked to complete the Patient Debriefing and Blinding Assessment survey immediately after V1. The blinded RA will dispense a 30-day asthma diary (4th grade reading level) to all subjects after each data collection visit. The Doser™, an electronic monitor capable of recording 30-days ICS use, will be attached to compatible ICS. Due to unique delivery systems for ICS, there is no single electronic device to monitor all ICS types. No change in ICS is required to participate in the Doser tracking log. Finally, we will collect patient satisfaction using the Client Satisfaction Questionnaire-8 (CSQ-8) at 3-months..

**CP measures.** PCPs will be asked to complete a demographic and professional history form and one survey at the time they sign informed consent: the Provider Co-Management Index (PCMI). The PCMI is a measure of PCP shared management. All PCPs will also be asked to complete the Provider Debriefing survey immediately after V1.

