#### Content of Data and Safety Monitoring Report

The Data and Safety Monitoring Report will include the following items:

1. Narrative/Trial Summary including study status; minutes of SMC consultations (action items, resolution of action items), and summary of any protocol changes.
2. Study Administration Recruitment and Participant Status including tables reporting overall study status, actual vs. expected enrollment, participant enrollment status by condition, overall reasons for eligibility

screen failures, overall protocol deviations, protocol deviations by condition, demographic and key baseline characteristics, participant attrition by condition, and study duration for all participants.

3. Study Administration Data including tables reporting overall summary of assessment measures collected, assessment measures collected by condition, overall summary of missing outcome measures, missing

outcome measures by condition.

4. Safety Assessments for All Participants including tables reporting incidence of adverse events and severity of adverse events overall, as well as incidence of adverse events and severity of adverse events by condition.

**d. For multi-site studies, procedures to ensure compliance with the monitoring plan and reporting requirements across study sites.** As described above we

offer a robust plan for Auditing Selected Cases. In addition, consenting and data collection will be conducted by the same research assistant.

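### Table 1 lets the unblinded Project Manager take the phone ACQ6 that decides entry, and no ACQ symptom items are scheduled at Visit 1, so that call is by inference the only baseline for the primary outcome

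*Combined protocol and SAP*

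**What the plan says.** Three places give patient data collection to blinded staff. Survey Administration states "The RA (blinded) will be responsible for all patient data collection". Statistical Procedures says that trained RAs, "blind to treatment status, will collect data four times: baseline and 1-month, 2-month, and 3-month follow-up". Section d of the DSMP says that "consenting and data collection will be conducted by the same research assistant".

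The data-collection table under Survey Administration (the Table 1 to which the text refers) differs in two rows. It lists the RA or the Project Manager as collector for the phone ACQ6 and for Demographics. The Blinding paragraph says "The PI, Project Manager and database manager will not be blinded".

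The ACQ6 call is the first of two entry steps ("ACQ screen by phone and + CAM-A screen at visit"), with 1.5 as the cut-off. The ACQ is also the primary outcome: "The primary outcome measure is patient-reported asthma control over 3 months as measured with the ACQ". In the table, the ACQ6 is marked once, before Visit 1. At Visit 1 only the FEV1 item is marked. The row "Asthma Control Questionnaire – 7 items (ACQ7) with FEV1" is marked at Visits 2, 3 and 4.

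**The concern.** Randomization is by provider, and BREATHE providers are trained, tested and followed up before the first patient is enrolled. Someone who knows the provider assignments therefore knows a patient's arm from the provider's name. The Blinding paragraph hides the arm from the RA with codes and hold screens. Allowing the Project Manager to make the call bypasses that protection at the step that decides who enters.

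Differential entry after provider randomization is not repaired by the randomization. If the same call also supplies the baseline, a shift in recorded scores would carry into any contrast that uses baseline. Even with a blinded caller, that baseline would differ from follow-up in mode (phone against paper), version (six items against seven) and date (an unstated interval before Visit 1).

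**Working it through.** **1. Who collects.** Three statements say blinded RA. Two table rows say RA or Project Manager. The Project Manager is unblinded. The table gives the other patient questionnaires and the spirometry to the RA alone, so the exception falls on the instrument that is both entry test and primary outcome.

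**2. Which ACQ can serve as baseline.**

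| Time point | ACQ content in the table | Collector |
|---|---|---|
| Before Visit 1 | Six symptom items, phone | RA or Project Manager |
| Visit 1 | FEV1 only | RA |
| Visits 2, 3, 4 | Seven items, paper and spirometer | RA |

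Statistical Procedures counts four data collections including baseline, and Power & Sample Size assumes four repeated observations. Only three full ACQs are scheduled. The fourth has to use the phone symptom items, alone or joined to the Visit 1 FEV1. The documents do not say so; it is an inference.

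**3. What a baseline shift would do.** The planned effect is d × SD = 0.5 × 0.76 = 0.38 points (Power & Sample Size). Assume, as an illustration, that BREATHE baselines are recorded 0.2 points too high, with follow-up unaffected:

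- Change from baseline, or a baseline-to-end time-by-group contrast: −0.20, which is 0.20/0.38 = 53% of the planned effect, in BREATHE's favour.
- Group effect averaged over four occasions: 0.2/4 = +0.05, which is 0.05/0.38 = 13%, against BREATHE.
- If only the six phone items shift and the baseline is a seven-item mean, multiply by 6/7. The first figure becomes −0.17.

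Each figure scales in proportion to the assumed shift.

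**4. Regression to the mean, equal in both arms.** Inputs: 69% of those screened are uncontrolled (Enrollment feasibility), taken here to mean at or above 1.5. Scores are assumed normal with the same mean and SD on both occasions. Then z = Φ⁻¹(0.31) = −0.496. With SD 0.76 this puts the screened mean at 1.5 + 0.496 × 0.76 = 1.88, but the SD cancels from the probability:

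P(Visit 1 < 1.5 | screen ≥ 1.5) = [0.31 − Φ₂(z, z; ρ)] / 0.69

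| Phone-to-Visit 1 correlation | Φ₂ | Share below 1.5 | Of 80 |
|---|---|---|---|
| 0.95 | 0.265 | 6.5% | 5 |
| 0.9 | 0.247 | 9.2% | 7 |
| 0.8 | 0.220 | 13.1% | 10 |
| 0.7 | 0.199 | 16.1% | 13 |
| 0.6 | 0.181 | 18.7% | 15 |

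The plan gives 0.8 for repeated measures over three months. It gives no value for the phone-to-visit interval.

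**The case against.** The strongest reply is that this is a wording slip. Three statements name the blinded RA and two table cells dissent. The table has other slips: it marks the CAM-A before Visit 1 although the text gives it at the visit, and it dates Visit 4 about four weeks after Visit 1. A mark for a Visit 1 ACQ may simply be missing. That is plausible, but staff work from the table, so it needs correcting on either reading.

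The route is also narrow. The symptom items are the patient's own answers, the RA takes the FEV1, and entry needs a positive self-scored CAM-A as well. This limits the exposure, though 97% are expected to pass the CAM-A, so the ACQ does nearly all the selecting.

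Feasibility is the stated primary goal, and DSMP section f says the trial is not powered for significance. But the analysis plans two-sided tests at 0.05, and the pilot is meant to supply effect sizes for a larger trial.

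Stronger readings a reader might infer, and why they fail:

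- *The 13% (10 of 80) measures arm-related bias.* It does not. It would arise equally in both arms under a fully blinded caller.
- *The phone score weakens a planned baseline covariate.* The analysis section names no baseline ACQ covariate.
- *Telling the provider the ACQ score biases the comparison.* Providers in both arms receive it, and no arm-related mechanism is evident.

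**Conclusion.** The point holds as an internal contradiction and a gap in the schedule. The table permits an unblinded person to score entry on the primary-outcome instrument, and it schedules no other pre-intervention ACQ symptom score. That the phone ACQ6 would be the analysis baseline is inferred from the schedule, not stated.

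The documents do not show that the Project Manager will make calls or that any score will be shifted, and the opening closes if the RA makes every call. The size of any bias is unknown. For an assumed 0.2-point shift in one arm it ranges from about 0.05 to 0.20 points against a planned 0.38, depending on the contrast. Separately, about 6–19% of patients passing the screen (5–15 of 80) would score below 1.5 at Visit 1, under the normality assumption and correlations of 0.95 to 0.6. This bears on how baseline is described, not on arm-related bias.

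**What to change.** 1. In the data-collection table, change the collector of the phone ACQ6 and Demographics to the blinded RA only.
2. Add the six ACQ symptom items at Visit 1, given on paper by the blinded RA before the provider encounter. Name that score, with the same-day FEV1, as the baseline ACQ in Statistical Procedures, and keep the phone score for eligibility only.

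Both are needed. The first protects entry; the second protects the baseline and aligns its mode and version with follow-up.

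The cost is table edits, one sentence in the analysis section, six more items at Visit 1, and all screening calls falling to the RA. The sample size does not change. Some enrolled patients will have a recorded baseline below 1.5: the change records regression to the mean but does not prevent it. It also leaves untouched the earlier step in which clinic staff contact patients before the study team does.

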## PHASE II ONLY

### Study Procedures

#### Pilot Randomized Clinical Trial Phase

**Study Procedures: PCP Recruitment, Consent and Randomization.** Randomization will be at the level of the PCP. This is a two-group randomized trial with outcomes analyzed at the patient level. We will randomize 8 PCPs (4 / FQHC site) into **BREATHE** and attention control conditions stratified for provider type (physician vs. nurse practitioners [NPs]/physician assistant [PAs]) to insure equal numbers of PCPs within each PCP type are assigned to each condition. Randomization lists will be computer generated in advance by our data manager (allowing the biostatistician to remain blinded during analysis). We do not anticipate difficulty in recruiting 4 PCPs/FQHC since one FQHC has ~15 PCPs (10 physicians and 5 NPs/PAs) and the other has 35 (20 physicians and 10 NPs/PAs).

**Provider Consent.** After reading the informed consent and having questions addressed, PCPs will be asked to sign informed consent indicating they are entering the study voluntarily. Declinations to enroll, if any occur, will be a metric that we will track. Consent will be obtained by either the PI or the Project Manager as these individuals are unblended.

**Inclusion Criteria:** PCPs (MDs and NPs/PAs) working in family, primary or internal medicine care services who have at least 40 adult patients with persistent asthma (defined as having been prescribed ICS) on their patient panel will be considered eligible for enrollment.

**Exclusion Criteria:** PCPs whose primary focus is outside of adult health services (family, primary or internal medicine), such as behavioral health, pediatrics and OB-GYN.

**Patient Recruitment.** We will recruit patients using methods we have used successfully in prior studies. The FQHC administrator will create a potential list of subjects using a combination of ICD-10 (Asthma 493)-specific queries of electronic membership records and searching of scheduled patient visits for the FQHC PCPs to review. The research team will receive only the names and contact information of those the FQHC clinicians have contacted and who agree to receive a call from the research team. We will also accept subjects who respond to posted recruitment flyers.

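### The blinded RA who consents patients and measures outcomes is also the named collector of the post-visit debriefing and blinding form, which could reveal a PCP's arm before that PCP's later patients are consented

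*Combined protocol and SAP*

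**What the plan says.** The allocation and staffing arrangements are spread over several sections.

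- **Allocation** (Pilot Randomized Clinical Trial Phase): "Randomization will be at the level of the PCP". The plan states "We will randomize 8 PCPs (4 / FQHC site) into" the two conditions, stratified by provider type "to insure equal numbers of PCPs within each PCP type are assigned to each condition". For patients: "We will enroll 80 Black adults with uncontrolled asthma (10 / PCP").
- **Consent** (same section): "Consent will be obtained the RA who is blinded". DSMP item d, on multi-site procedures, adds that "consenting and data collection will be conducted by the same research assistant".
- **The form** (assessment schedule under Survey Administration): the row "Patient Immediate post-visit debriefing and blinding assessment" is a paper survey, with the RA as collector and the patient as source, marked at Visit 1. Statistical Procedures, under patient subject measures, says that all patients will "also be asked to complete the Patient Debriefing and Blinding Assessment survey immediately after V1".
- **Other Visit 1 forms**: the RA is also the named collector of the provider's post-visit debriefing and the patient's SDMQ-9.
- **Outcomes**: the RA collects the ACQ7 with spirometry, the AQLQ and the MARS-A at Visits 2 to 4.
- **Safeguards** (Blinding paragraph): the RA does not know what the patient codes mean, hold screens hide the arm-specific tablet content, and the RA leaves the room and stays out of earshot. Adequacy of blinding, for both patient and RA, is assessed as a process outcome when the study ends.

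**The concern.** With allocation by PCP, a patient's assignment is concealed at consent only while the person obtaining consent does not know that PCP's arm. In an individually randomized trial, one patient's guess says little about the next patient. Here each form bears on every later patient of the same PCP. Balancing the arms within provider type also means that inferring some PCPs' arms narrows the possibilities for the others.

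The two visits differ plainly in content: one covers asthma beliefs and ICS use, the other diet and exercise. A form asking for the patient's impression of the visit and, as its title implies, a view on assignment could carry that difference to the RA minutes after the RA was kept out of the room to prevent it.

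Two things are at stake. An RA who can infer the arm might present consent differently, which is selection after cluster allocation. The RA might also coach spirometry differently at follow-up. Either would enter the effect-size estimates that the pilot is meant to supply for a larger trial. The PCP and patient random effects in the mixed model would not remove it.

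**Working it through.** The plan gives no figure on this point, so there is nothing to reproduce. The check has three parts.

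**1. Is the route open in the text?**

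| Link | Where stated |
|---|---|
| Arm is common to all patients of a PCP | Pilot Randomized Clinical Trial Phase |
| RA obtains consent and collects the data | Same section; DSMP item d |
| RA collects the form at Visit 1 | Survey Administration schedule |
| Form completed straight after the visit | Statistical Procedures |
| Tablet and conversation hidden from RA | Blinding paragraph |
| Completed form hidden from RA | Not stated anywhere |

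Every link but the last is stated. Nothing provides for sealing, a different collector or later collection. The end-of-study blinding check can detect a leak but cannot prevent one.

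**2. How many patients could be exposed?** Inputs: 8 PCPs, 10 patients each. If each PCP's patients are enrolled one after another, those consented after at least one earlier form from the same PCP number 8 × (10 − 1) = 72, and 72 / 80 = 90%. This is an upper figure, because overlapping enrolment would lower it. Separately, every Visit 2 to 4 measurement is taken after that patient's own form.

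**3. How well could the RA predict the arm?** This depends on q, the probability that one form points to the correct arm. The documents do not give q, so it is an assumption, taken over 0.5 to 0.9. Suppose the RA follows the majority of k earlier forms from the PCP, with ties settled by a coin flip. Then

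P(correct) = Σ over x > k/2 of C(k,x) q^x (1−q)^(k−x), plus half the probability of a tie.

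Example with k = 3 and q = 0.7: 3 × 0.7² × 0.3 + 0.7³ = 0.441 + 0.343 = 0.784.

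| q (assumed) | k = 1 | k = 3 | k = 5 | k = 9 | Mean over patients 2–10 | Of 72 |
|---|---|---|---|---|---|---|
| 0.5 | 0.50 | 0.50 | 0.50 | 0.50 | 0.50 | 36 |
| 0.6 | 0.60 | 0.65 | 0.68 | 0.73 | 0.668 | 48.1 |
| 0.7 | 0.70 | 0.78 | 0.84 | 0.90 | 0.810 | 58.3 |
| 0.8 | 0.80 | 0.90 | 0.94 | 0.98 | 0.910 | 65.5 |
| 0.9 | 0.90 | 0.97 | 0.99 | 1.00 | 0.969 | 69.8 |

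The table shows that modest information per form accumulates within a PCP. It does not show that the forms are informative. It also assumes independent guesses and equal accuracy in both arms. If 70% of patients in both arms guessed active, accuracy would be 0.7 in one arm and 0.3 in the other, averaging 0.5. A majority rule would then tend to label every PCP active.

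**The case against.** The strongest reply is that the mechanism is inferred. The form is not in the documents, so the arm guess is read from its title. Being named as collector does not mean the RA reads the answers. The control is a matched 7-minute discussion designed to keep patients blinded, so q could be near 0.5. All of this stands, and it limits the point to an unprotected route.

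The RA's discretion is also limited. Apart from flyer responders, candidates are first approached by health-center clinicians. The ACQ entry criterion is a fixed cut-off that the RA or the Project Manager may administer. The CAM-A scores itself, and any one endorsement qualifies. The plan does not say who judges the mental-health exclusion. The follow-up questionnaires are on paper, which leaves spirometry coaching as the clearly effort-dependent measurement. This stands too. The manner of presenting consent remains open, but its effect cannot be sized.

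The RA also receives the provider debriefing and the SDMQ-9 and meets patients again at follow-up, so protecting one form closes only part of the leak. That is right, and it argues for handling these forms together.

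Finally, the trial's primary goal is feasibility, and learning whether blinding holds is part of that. But the pilot is also meant to yield effect sizes, and a check at the end of the study protects neither consent nor measurement. Statistical Procedures refers to RAs in the plural, whereas DSMP item d has one assistant doing both tasks. On either reading, blinded RAs collect both the form and the outcomes.

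**Conclusion.** The point holds as a gap in the protection of blinding and concealment, and it is cheap to close. Its size is unknown. Up to 72 of 80 patients (90%) would be consented after an earlier form from the same PCP, if enrolment within PCPs is sequential. The RA's ability to predict the arm runs from 50% when the forms are uninformative up to the assumption-dependent values tabulated above.

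A reader might infer two stronger things. One is that the plan's own procedure defeats its blinding. The documents do not support that, because they show neither the form's items nor that the RA reads the answers. The other is a specific bias on the primary outcome. One could posit a shift of 0.1 to 0.2 ACQ points and divide by the plan's SD of 0.76 to get 0.13 to 0.26 SD. But the shift would be a free assumption with no link to the prediction rates, so no ACQ bias figure should be attached to this point.

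**What to change.** In the Survey Administration schedule and under patient subject measures in Statistical Procedures, state that:

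- the patient completes the debriefing and blinding form privately and seals it in an ID-labelled envelope;
- the envelope goes unopened to the Project Manager or data manager, both already unblinded, for entry;
- the RA does not read, administer or enter the form.

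Apply the same handling to the provider's post-visit debriefing, and to the SDMQ-9 if it is completed after the visit; the schedule does not say which.

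If a patient needs help reading, use someone at the site who neither consents patients nor assesses outcomes and does not know the arm. Otherwise accept the item as missing. A later phone call from the Project Manager is not a good substitute. It conflicts with completion straight after the visit, and an unblinded person eliciting the guess could influence it.

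The cost is a few lines of text and some envelopes. The RA loses the on-the-spot completeness check, so a few more items may be missing. Other contact between the RA and patients at follow-up remains, so this lowers the risk without removing it.
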